### **Data Analysis for COVID-19 Pilot Cohort.**

The objectives of the analysis are consistent with the UH3 study design to evaluate the influence of virtual prevention navigation on progress toward a number of health goals. However, given the restricted timeline for prevention navigation with two assessments one month apart, we will assess pre-and post-changes in factors associated with the risk of HCV, HIV, and overdose death among PWID.

## **7.0 STATISTICAL CONSIDERATIONS**

**Sample size and power considerations for Aim 1.** Power to detect a significant impact of the client-centered prevention home model is based on the change in proportion of clients in the 3 target counties who receive the 9 essential services (see Table 1, pg. 2) compared to clients in the 3 non-targeted counties. The design effect for respondent-driven sampling is a complex function of the network structure in the population, and thus, it is difficult to precisely estimate the sample size requirements. Nevertheless, simulation research indicates that the design effect for respondent-driven sampling is likely to be 2 or less, which suggests that a sample twice that of simple random sampling should provide adequate power. We estimate that approximately 10% of all clients will have access to all 9 essential services prior to the study. Applying a design effect of 2, and given a sample size of 800-1200 clients, the study will be powered to detect an increase in service provision of 8-10% (424 subjects per group is sufficient to detect a 10% difference in essential service provision rates; 582 subjects per group is sufficient to detect an 8% difference), assuming 80% power and 5% type I error.

**Sample size and power considerations for Aim 3.** The complexity of our study design requires multiple longitudinal approaches to account for independent and dependent samples. Based on our formative work, an average of 2 clients enrolled per week into the study is feasible for the SSP staff.

With a sample size of 405 (270 intervention and 135 controls), we would have 80% power to detect a difference between 28% and 42% in the same outcome, an effect size that we believe is meaningful and realistic to achieve. In other words, the sample size was chosen to ensure that the Primary Aim 1 comparisons of “Strongly Agree” vs all others of a factor would have sufficient power to detect clinically meaningful increases in accessibility. To address Primary Aim 1, we used preliminary data from the first phase of the study to assume that the base rate of a participant who will strongly agree that it is easy for them to access addiction treatment services is 26%.

**COVID-19 Pilot.** Given the uncertainty of the timeline for prevention navigation, it is unclear how large our sample size will be. Understanding that there will be two assessments one month apart, we will use matched pair t-test to assess differences between the first and second assessments. Using the same process as above, comparisons of “Strongly Agree” vs all others of a factor would have sufficient power to detect meaningful increases in accessibility. We expect a total sample size of 216 PWID, which provides adequate statistical power (0.83) to detect a 20% difference between three time points of interest (two-sided alpha=0.05).

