## STUDY SUMMARY

In response to RFA-DA-17-014, HIV, HCV and Related Comorbidities in Rural Communities Affected by Opioid Injection Drug Epidemics in the United States: Building Systems for Prevention, Treatment and Control (UG3/UH3), our research team has proposed a multi-phase, mixed-methods study that aims to implement and evaluate a novel community response model, which we have named the Community-Based, Client-Centered Prevention Home.

Using the organizational infrastructure of a large, multi-site syringe service program serving a geographically disperse population of people who inject drugs in rural communities across Northern Wisconsin, we will build locally responsive systems to facilitate uptake of evidence-based prevention services for high-risk clients. The Client-Centered Prevention Home model incorporates prevention case management and mobile health information technology into traditional harm-reduction services delivered at syringe service programs, which we hypothesize will increase use prevention services. During the first 2 years the project (UG3 phase), we will perform needs assessments in 6 rural Wisconsin counties in partnership with local stakeholders, and use respondent driven sampling to conduct a cross-sectional epidemiologic evaluation to estimate the prevalence of HIV, viral hepatitis and sexually transmitted infections. Contingent upon meeting recruitment and data collection goals, during years 3-5 (UH3 phase) of the project we will deploy and evaluate the Client-Centered Prevention Home model in the 3 counties demonstrating highest vulnerability to worsening epidemics of opioid injection. The 3 remaining counties not selected for implementation will serve as comparison sites in a quantitative evaluation of program effectiveness during year 5.

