**Aim 3:** To evaluate the impact of the Client-Centered Prevention Home model, deployed within syringe service programs in counties with high burden of injection drug use, on the proportion of clients who receive the package of 9 essential services endorsed by the World Health Organization to prevent HIV/HCV in people who inject drugs. We will use input from local stakeholders and a proven implementation science framework (NIATx) to translate lessons learned through Aims 1 and 2 into a service model that is responsive to the unique needs of rural residents and adaptable to communities with varying degrees of resource limitation.

This project will be conducted by an experienced, interdisciplinary team working across academic, public health, and non-governmental sectors. The main community partner Vivent Health, formerly known as the AIDS Resource Center of Wisconsin (ARCW), is a unique, state-wide organization that provides harm reduction services, including syringe services and confidential HIV and HCV testing, to clients at 10 fixed sites and numerous mobile units reaching all 72 Wisconsin Counties. Based on our preliminary studies and prior collaborations, we have selected 6 rural counties as the focus of the epidemiologic evaluation and community needs assessment during the UG3 phase. Contingent upon meeting recruitment and data collection goals, in the UH3 phase of the project we will select the 3 counties demonstrating the highest need, then deploy and evaluate the Client-Centered Prevention Home model at Vivent Health field offices located within these service areas. Service areas not selected for implementation will serve as comparison sites in the assessment of program effectiveness during Year 5.

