## Study Phases

Phase 1 (UG3) September 2017 – August 2019
 
Study activities
 
 
• Creation of working groups
 
• Building stakeholder support in 6 target communities
 
• Client survey and seroprevalence study in syringe service programs
 
• Community needs assessment
 
	
Phase 2 (UH3) September 2019 – August 2023
 
Study activities
 
 
• Development of Prevention Case Management Protocol
 
• Enrollment of syringe service program clients in Prevention Case Management Program at 3 Vivent Health offices
 
• Adaption of A-CHESS mobile health application (2021 Pilot).
 
• Virtual Prevention Navigation Implementation Cohort Study (during COVID-19 Pandemic)
 

Additional Phase 1 Activities (UG3) February 2022 – December 2023
 
Study Activities
 
 
• Link UG3 data with several registries from the WI Department of Health Services to ascertain longitudinal outcomes of interest during the COVID-19 pandemic
 
• Quantify rates of COVID-19 infection, testing, vaccination, and mortality from DHS data
 
• Quantify fatal overdose rates and nonfatal overdose hospitalization rates
 
• Quantify hepatitis A and B vaccination prevalence
 
	

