## 4.0 REGISTRATION PROCEDURES

### Participant recruitment for Aim 1 (UG3 Phase).

Using a cross-sectional study design, we will enroll 1,200 people who inject drugs to get high and live in rural communities. Based on the volume of syringes distributed in 2016 at the six rural Vivent Health offices listed above, we anticipate enrolling 200 individuals at each site.

**Eligibility screening and enrollment of seeds.** Individuals will be eligible for enrollment if they are 15 years of age or older, have injected any drug to get high in the past 1 month, and reside in a rural community. Rural residence will be determined by ZIP code, which will be programmed in the screening instrument on REDCap. The system will classify the ZIP code as rural if the ZIP Code RUCA Approximation is >4 or the participant lives in a catchment ZIP code for the SSP.

A research assistant will screen clients for eligibility, either on site at Vivent Health or by phone. Vivent Health staff will notify clients of the opportunity to speak with research staff by phone if they

report living in a rural community, are 15 or older, and are actively injecting drugs. To minimize the involvement of Vivent Health staff in the screening process at sites where having Vivent Health staff engaged in research would interfere with routine prevention activities, we have developed a flexible screening process that can be done without the involvement of Vivent Health staff. At certain sites, Vivent Health staff may become engaged in research and fulfill the research assistant role for the purpose of screening, if the agency determines this is the best strategy for managing the flow of clients and study participants. Specifically:

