### **Participant recruitment for Aim 3 (UH3 Phase, 2019-2021).**

Based on preliminary data, burden of opioid-related illness, and familiarity with supportive local stakeholders, we selected La Crosse County, Marathon County, and Brown County as the implementation sites for this study. Eau Claire, Douglas, and Outagamie Counties will serve as the

nonintervention sites, where participants will receive services as usual. In the fall of 2019, 3 full-time Prevention Navigators were hired and trained to conduct the intervention. Participants in this phase of the study will be recruited into one of two groups, Prevention Navigation, or usual services. Beginning in year 3, SSP clients at the 6 selected Vivent Health sites will be notified about the study by prevention specialists or SSP staff if the client 1) tests for HCV or HIV at the SSP, 2) inquires about services that may be in the prevention home through casual conversation, 3) the client engages in naloxone training, 4) through posted materials of the availability of new resources for improving prevention services and linkages to treatment in the SSP and community offices, 5) recruit through flyers and posted materials in the SSP and local community resource offices, and public areas, 6) through Vivent Health Facebook advertisements, 7) through our study website listed on our flyers, and/or 8) through respondent-driven sampling (RDS). Upon the completion of the first two attended Prevention Navigation sessions,

participants will be given a referral coupon and asked to refer one eligible peers per coupon to participate in the study. Vivent Health will dispense coupons that have been prepared by UW research staff. SSP clients at the nonintervention sites will be recruited at the time the Vivent Health staff member assists them with regular exchange services. Nonintervention sites will aim to enroll about one participant every-other week.

[figure not shown]
[figure not shown]

Figure 5. Parallel crossover (wait-list control) and cross-site study design

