## **Benchmarks for progressing to UH3 phase.**

If the research proposed above is successful, by the end of year 2 we will have established estimates of the burden of infectious diseases in six rural counties, and described service gaps that must be filled in order to ensure that people who inject drugs have access to the complete package of prevention services. We believe that transition to the UH3 phase of the study, which is described below, will be justified if we achieve the following milestones: (1) ***Client reachability:*** We will enroll no fewer than 800 SSP clients who reside in rural communities during the 12-month recruitment period of the UG3 phase. Based on current and historical volume of prevention encounters at Vivent

Health offices, we expect to be able to achieve the recruitment target of 1,200 individuals without difficulty. However, if enrollment is substantially slower than expected, we believe that recruiting at least 2/3 of this number will demonstrate our ability to engage SSP clients in sufficient numbers to answer our research questions and guide implementation of the Client-Based Prevention Home model. (2) **Local service capacity:** We will confirm there are sufficient resources in at least 3 of the 6 targeted counties to ensure it is feasible that SSP clients can utilize all 9 of the essential prevention services. For example, we might not be able to move forward with implementation of the service delivery model if we cannot identify providers who provide MAT or are willing to start provision of this service with support and consultation from the UW Addiction Medicine Program (see “Provider-level interventions” below). (3) **Community stakeholder willingness:** We will confirm that key stakeholders (e.g., MAT providers, County Public Health Officers, Criminal Justice Agencies, others) are supportive of the new prevention services model participating counties. We will obtain letters of support if requested by funders.

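### The 8-10 point power claim for the nine-service outcome rests on the pre-intervention survey size; the 405 people who will be evaluated do not support its 8-point end, and Appendix 2 does not list the outcome

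*Combined protocol and SAP*

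**What the plan says.** Section 2.0 states Aim 3 as the impact of the prevention home "on the proportion of clients who receive the package of 9 essential services endorsed by the World Health Organization". The power statement for that outcome is in section 7.0, in the paragraph headed Aim 1. It contrasts the three target counties with the three non-target counties, takes 10% of clients as having access to all nine services beforehand, applies a design effect of 2, and says: "given a sample size of 800-1200 clients, the study will be powered to detect an increase in service provision of 8-10" percent, at 80% power and 5% type I error. It gives 424 per group for 10 points and 582 per group for 8 points.

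The sizes 800 and 1,200 appear elsewhere only for the UG3 phase. Section 4.0 says: "Using a cross-sectional study design, we will enroll 1,200 people who inject drugs to get high and live in rural communities". The progression benchmark in section 6.0 says: "We will enroll no fewer than 800 SSP clients who reside in rural communities during the 12-month recruitment period of the UG3 phase".

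Appendix 1, section 1.6, sets the sample for evaluating the intervention at 405: 270 at intervention sites and 135 at non-intervention sites. Section 1.7 of that appendix compares them within person and between sites. The Aim 3 paragraph of section 7.0 gives 80% power for 28% against 42% with this sample. It calls this the same outcome, but then describes strong agreement that addiction treatment is easy to access.

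Section 6.0 refers the reader to Appendix 2 for the Aim 3 outcomes. Appendix 2 lists single survey items, program and claims measures and county-level rates. None is receipt of, or access to, all nine services.

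**The concern.** A power statement about an intervention effect needs outcome data collected after the intervention. The sample behind this one is a cross-sectional survey taken before navigation began, under an aim that section 6.0 calls descriptive. Two places hint at a later comparison. The Study Summary says: "The 3 remaining counties not selected for implementation will serve as comparison sites in a quantitative evaluation of program effectiveness during year 5". Section 2.0 repeats: "Service areas not selected for implementation will serve as comparison sites in the assessment of program effectiveness during Year 5". Section 6.0 adds that UG3 data will supply baseline values for UH3. None of these gives a follow-up sample size. The UH3 activity list has "Enrollment of syringe service program clients in Prevention Case Management Program at 3 Vivent Health offices" but no repeat survey, and neither does the timetable in Appendix 1.

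A reader would therefore credit the trial with 8-10 point sensitivity on the outcome named in its objective, although the described evaluation sample is about a third to a half of the size behind that figure (405/1,200 = 34%; 405/800 = 51%).

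The outcome itself is also unsettled. Section 7.0 counts services received but takes its base rate from clients who have access to them. Table 6 records perceived access on Likert scales. Appendix 1, section 1.3, restates the aim without the number nine.

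**Working it through.** **Inputs.** Base rate 10%, increases of 8 and 10 points, design effect 2, 80% power and 5% type I error: section 7.0, Aim 1 paragraph. Groups of 270 and 135: section 7.0, Aim 3 paragraph, and Appendix 1, section 1.6. Assumptions made here: two-sided test (the paragraph does not say), no dropout and, in step 2, no design effect.

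**Formula.** Power = Φ[(d − 1.96·s0)/s1]. Here d is the difference and s1 = √[p1(1−p1)/n1 + p2(1−p2)/n2]. For the pooled test s0 = √[p(1−p)(1/n1 + 1/n2)], with p the weighted mean proportion. For the unpooled test s0 = s1.

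**Step 1: the plan's own figure.** Split evenly and divided by the design effect of 2, 800 clients are 200 effective per group and 1,200 are 300. The increases detectable at 80% power (pooled) are 9.97 and 7.91 points, so the stated 8-10 is what 800-1200 delivers. The per-group figures total 2 × 424 = 848 and 2 × 582 = 1,164, inside that range. The 582 reproduces (583 unpooled, 590 pooled). The 424 is somewhat more than the 398 that the pooled formula gives, which does not affect the point.

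**Step 2: the 405.** With n1 = 135, n2 = 270 and p1 = 0.10:

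- 8 points (p2 = 0.18): p = 0.1533, s0 = 0.03798, s1 = 0.03483. Pooled: (0.08 − 1.96 × 0.03798)/0.03483 = 0.16, power 56%. Unpooled: 0.08/0.03483 − 1.96 = 0.34, power 63%.
- 10 points (p2 = 0.20): p = 0.1667, s0 = 0.03928, s1 = 0.03549. Pooled: (0.10 − 1.96 × 0.03928)/0.03549 = 0.65, power 74%. Unpooled: 0.10/0.03549 − 1.96 = 0.86, power 80%.
- Increase detectable at 80% power: 10.8 points pooled, 9.9 unpooled.

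Exact enumeration of the pooled test gives 57% and 75%. At 2:1 allocation, 8 points would need 603 people (unpooled) to 682 (pooled).

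**Step 3: sensitivity to assumptions the documents do not settle** (pooled unless noted).

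| Assumption | Power, +8 points | Power, +10 points | Detectable increase, points |
|---|---|---|---|
| One-sided test | 69% | 84% | not computed |
| Dropout 10% | 52% | 69% | 11.5 |
| Dropout 30% | 42% | 58% | 13.3 |
| Design effect 2, intervention arm only (135/135 effective) | 47% | 64% | 12.5 |
| Design effect 2, both arms (135/67.5 effective) | 30% | 43% | 16.3 |
| Between-site difference in change (unpooled), correlation 0 / 0.3 / 0.5, controls staying at 10% | 40 / 53 / 67% | 56 / 71 / 84% | not computed |

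The both-arms row is an outer bound. Referral chains are one of eight recruitment routes in section 4.0, and for controls it says: "SSP clients at the nonintervention sites will be recruited at the time the Vivent Health staff member assists them with regular exchange services".

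**Step 4: the 405's own power statement.** For 28% against 42% with 270/135, power is 79% pooled and 82% unpooled. That statement reproduces, but it concerns a different outcome.

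**The case against.** **The plan never says that 405 detects 8-10 points.** It ties that range to 800-1200, and the arithmetic holds; the 405 has its own outcome and effect. This is fair as far as it goes. But the paragraph presents the range as power to detect the impact of the prevention home, and no described post-intervention sample has that size. The protocol's statement that there is no single primary outcome does not supply one.

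**The shortfall is narrow.** At 10 points it is: the unpooled formula just reaches 80%. At 8 points every between-site variant in the table falls short, including the one-sided test.

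**Repeated measures could help.** In the within-person comparison of the 270 (8 points, no dropout), power is 77%, 89% and 96% at assumed correlations of 0, 0.3 and 0.5. That comparison has no control group and cannot stand in for a contrast between counties. A baseline-adjusted between-site model scales the required size by 1 − r². To bring 682 down to 405, r² must be 1 − 405/682 = 0.406, so r is about 0.64; starting from 603, r is about 0.57. The documents give no correlation.

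**The survey already asks about access.** Appendix 3 lists access items for condoms, syringes, naloxone, buprenorphine, vaccination and treatment of HIV, HCV and STIs, and the UH3 survey is adapted from that instrument. These items measure access rather than receipt, tuberculosis is not among them, and no composite is defined.

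**Some design material is not visible.** The design figure in section 4.0 is not shown in the text reviewed, and section 6.0 points to a section 3.5.4 that does not appear there. A year-5 sample may therefore be intended. The finding is that the available text describes none.

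**Conclusion.** The concern holds. The 8-10 points are correct for 800-1200 clients with a design effect of 2, but that is the pre-intervention survey. For the 405 to be evaluated, a simple between-site comparison from a 10% base has 56-63% power for 8 points and 74-80% for 10, with a detectable increase of 9.9 to 10.8 points. These figures assume a two-sided 5% test, no dropout and no design effect; dropout or a design effect makes them worse. A baseline-adjusted analysis could close the gap at 8 points only with a correlation of about 0.57 to 0.64, which the documents do not support or exclude. Separately, the outcome named in the Aim 3 objective has no row in the table of Aim 3 outcomes, and the text moves between services received and services accessible. The 28% against 42% statement for the 405 is not disputed.

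**What to change.** 1. In section 7.0, remove the intervention-effect claim from the Aim 1 paragraph, or restate it for 270/135, naming the analysis and giving any design effect, dropout or correlation as an assumption. If a year-5 sample of 800-1200 is intended, describe its recruitment, timing and analysis.
2. Reconcile section 2.0, section 7.0 and Appendix 1, section 1.3, with Appendix 2. Either add a defined nine-service outcome, stating consistently whether it means receipt or perceived access, or reword the Aim 3 objective to the outcomes that are measured.
3. In the Aim 3 power paragraph, replace the reference to the same outcome with the item on which the 405 was sized. Appendix 2 has separate methadone and buprenorphine access items and none worded for addiction treatment in general, so the item meant should be named.

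The cost is mainly protocol and SAP wording, and the stated detectable effect becomes somewhat less favourable. If a receipt composite is kept, new questionnaire items may be needed, because Table 6 records perceived access only.

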### 5.1.1 Additional Data Collection for DHS Linkage Study on COVID-19 Pandemic Impact Among UG3 Participants

We will use data collected by the Wisconsin Department of Health Services (DHS) to estimate the rates of COVID-19 infection, testing, hospitalization, and death, fatal and nonfatal drug overdoses, and vaccination against COVID-19, Hepatitis A and Hepatitis B in the UG3 cohort. To achieve our objectives, we propose a retrospective cohort study that will be facilitated by linking data from several DHS registries with UG3 participants. We propose to provide DHS colleagues with identifiable data from 991 of our prior research participants (identifiers: participant name, date of birth, gender, race, ethnicity, previous address, previous phone number, date of participation in our study) to facilitate linkage with several DHS registries. We are seeking approval for the DHS data linkage via a partial waiver of authorization, waiver of consent, and by maintaining a log of the protected health information provided to DHS per standardized disclosure logs (see here: <https://compliance.wisc.edu/wp-content/uploads/sites/102/2019/02/Accounting-for-Disclosures-Log-Research.pdf>). The linkage process is described below:

1. UW will provide a dataset containing a unique study identification number and participant name, date of birth, gender, race, ethnicity, previous address, previous phone number, and date of study participation to colleagues at DHS.

2. DHS will link identifiers with vital records data to identify the date (from study participation date through present day) and cause of any deaths that have occurred among participants of our prior study, from study participation date through present day.
3. DHS will link identifiers with COVID-19 data captured in WEDSS to identify the date of any COVID-19 tests, confirmed or probable infections, and hospitalizations.
4. DHS will link identifiers with WIR to identify the dates of all COVID-19 vaccination doses received and type of vaccine (brand or whether an mRNA/adenovirus vector vaccine).
5. DHS will link identifiers with WIR to identify the dates of all vaccine doses for hepatitis A or B received (including doses received before study participation, if possible).
6. DHS will link identifiers with hospitalization data to identify overdose events involving an emergency department visit or hospitalization.

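### The Aim 1 power statement names a change compared between county groups but is sized as a one-time difference, and its 424 per group does not fit the method that gives 582

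*Combined protocol and SAP*

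**What the plan says.** Section 7.0, in the paragraph on sample size and power for Aim 1, states that power to detect an effect of the intervention is "based on the change in proportion of clients in the 3 target counties who receive the 9 essential services". The reference group is the other three counties ("compared to clients in the 3 non-targeted counties"). It assumes that "approximately 10% of all clients will have access to all 9 essential services prior to the study". Taking a doubling of the sample for respondent-driven sampling and a total of 800 to 1,200, it concludes that "the study will be powered to detect an increase in service provision of 8-10" percentage points. The supporting parenthesis says "424 subjects per group is sufficient to detect a 10% difference in essential service provision rates" and gives 582 per group for an 8-point difference. Power is 80% and type I error 5%; sidedness is not stated.

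The 800 is the minimum enrolment milestone in section 6.0 (benchmarks for progressing to UH3), and 1,200 is the target in section 4.0, at 200 per site. Section 6.0 (data analysis for Aim 1) calls Aim 1 descriptive, but adds that its data supply the baseline values for later pre/post analyses in UH3.

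**The concern.** There are two separate faults in one paragraph.

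First, the two per-group figures should come from one method, and they do not appear to. The 10-point figure also implies a total above the lower end of the range that it is meant to support.

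Second, a change in one set of counties set against the change in another involves four estimated proportions, while the quoted figures involve two. The counties are chosen, not randomised, so equal baselines cannot be taken for granted, and the pre/post use of the Aim 1 data suggests that the word change is meant literally. If so, the variance is larger than the one used and the 80% is attached to the wrong contrast. This is the plan's only power statement for the proportion receiving all nine services, which is the outcome named in Aim 3. The Aim 3 power statement uses a different outcome, strong agreement that a service is accessible.

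**Working it through.** **Inputs.** From section 7.0: base rate 10%, design effect 2, rise of 8 or 10 points (to 18% or 20%), 80% power, 5% type I error. From sections 4.0 and 6.0: 1,200 target and 800 minimum. With three counties against three and equal numbers per site, that is 400 to 600 per group. Assumed here: two-sided test, so (1.960 + 0.842)² = 7.849.

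**Step 1. Reproduce the plan's figures as a one-time difference.** Unpooled: n per group = 2 × 7.849 × [p1(1−p1) + p2(1−p2)] / d².

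- 8 points: 2 × 7.849 × (0.09 + 0.1476) / 0.0064 = 582.8. This is the plan's 582.
- 10 points: 2 × 7.849 × (0.09 + 0.16) / 0.01 = 392.4. This is not 424.

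| Method | 10 points | 8 points |
|---|---|---|
| Plan | 424 | 582 |
| Unpooled | 392 | 583 |
| Pooled under the null | 398 | 588 |
| Continuity-corrected (unpooled to pooled) | 432–437 | 632–637 |

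Fisher's exact test gives 79.7% power at 424 for 10 points, which is close, but only 76.8% at 582 for 8 points. One-sided formulas for 10 points give 314, or 354 with continuity correction. No single method tried yields both figures.

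**Step 2. Does 800 suffice for a one-time difference?** 2 × 424 = 848 > 800, but the surplus comes from 424 being too large.

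- 400 per group (effective 200), 10 points: SE = √(0.25/200) = 0.0354; power = Φ(0.10/0.0354 − 1.960) = 80.7% (80.2% pooled).
- 600 per group (effective 300), 8 points: SE = √(0.2376/300) = 0.0281; power = 81.1% (80.8% pooled).

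So the link from 800–1,200 clients to 8–10 points is sound for a one-time comparison.

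**Step 3. The contrast as worded: a difference in change.** Assume independent waves, n per group at each wave, comparison counties flat at 10%, and design effect 2 at both waves. Variance = [3 × 0.10 × 0.90 + p2(1−p2)] / (n/2); power = Φ(d/SE − 1.960).

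- 400 per group, 10 points: variance = (0.27 + 0.16)/200 = 0.00215; SE = 0.0464; power = Φ(0.197) = 57.8%.
- 600 per group, 8 points: variance = (0.27 + 0.1476)/300 = 0.00139; SE = 0.0373; power = Φ(0.184) = 57.3%.
- At the plan's own 424 and 582: 60.3% and 56.0%.

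The variance is 0.43/0.25 = 1.72 times (10 points) and 0.4176/0.2376 = 1.76 times (8 points) that of the one-time contrast.

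**Step 4. Vary what the plan leaves open.**

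| Assumption changed | 400 per group, 10 points | 600 per group, 8 points |
|---|---|---|
| None (as step 3) | 58% | 57% |
| 800–1,200 covers both waves together | 33% | 33% |
| Design effect 1.5 | 70% | 70% |
| Same people followed, correlation 0.5 | 85% | 85% |
| Design effect 1 | 86% | 86% |

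**Step 5. Difference in change detectable with 80% power.** Under the step 3 assumptions, solve d = 2.802 × SE(d): 13.3 points at 400 per group per wave and 10.7 points at 600. Detecting 10 or 8 points would need about 675 or 1,025 per group per wave. None of these figures allows for having only three counties per arm.

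**The case against.** The strongest reply is that the paragraph can be read as a follow-up comparison between county groups that share one baseline: it gives a single 10% for all clients, and the parenthesis speaks of a difference in rates. On that reading the formula fits, and 800 to 1,200 clients do deliver about 80% power. This stands, and it is why the point is a mismatch to resolve and not a demonstrated shortfall.

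Three stronger inferences are tempting, and the documents do not support them.

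- A reader might infer from 848 against 800 that the study is underpowered at its minimum enrolment. For a one-time 10-point difference it is not (step 2).
- A reader might infer that power is simply 57–58% and not 80%. That needs a second independent wave of equal size, flat comparison counties and a design effect of exactly 2. The plan gives no follow-up size or correlation for this outcome, and says that the design effect is likely to be 2 or less. Independent waves are plausible, since the baseline survey is cross-sectional, but they are not stated.
- A reader might put section 5.1.1's "identifiable data from 991 of our prior research participants" in as the achieved Aim 1 sample. That section gives it only as the number sent for registry linkage, with no split by county group, so it is not used here.

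It is also fair to say that Aim 1 is labelled descriptive and that Aim 3 has its own sample size of 405. That lowers the practical weight. It does not remove the fault, because this paragraph expressly claims power for the impact of the model.

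**Conclusion.** The point holds in a limited form. The figure of 424 is inconsistent with 582 under every single method tried, and it contradicts the 800 beside it; this is a minor numerical error with no loss of power for a one-time comparison. The more important fault is that the paragraph names a difference in change and computes a one-time difference. If the named contrast is the intended one, the 80% is not delivered under independent equal-sized waves, a flat 10% in comparison counties and design effect 2: power is about 56–60% across the per-group sizes considered. The inputs that the plan leaves open move this from about 33% to about 86%, so any single figure is conditional. Reaching about 80% or more needs assumptions that the paragraph does not make, such as repeated measurement of the same people with substantial correlation, or a design effect near 1. The latter would also undo the plan's own doubling of the sample.

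**What to change.** 1. Replace 424 with the figure from the method behind 582: 392 (unpooled). Alternatively, use the pooled formula for both, 398 and 588. Name the method and the sidedness.
2. Say which contrast the 80% applies to. Either state that 80% power for 8–10 points holds only for a single-time comparison between county groups, or restate the detectable difference in change as about 13.3 points (800 clients per wave) to 10.7 points (1,200 per wave).
3. If the second option is taken, state its assumptions alongside: number and size of waves, whether the same people are measured, the correlation, the comparison-county rate and the design effect.

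The cost is a text correction with no change to recruitment or data collection. Under the second option the stated detectable effect becomes less favourable.
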